1.4 Study Rationale

Treatment groups are TTP399 800 mg QD and placebo QD, which were selected based on prior clinical studies and research of currently available therapies and the results of the sentinel phase of the study, which evaluated doses up to 1200 mg. This study conforms to

regulatory guidance depicted in FDA adaptive design guidance: FDA guidance *Adaptive Design for Clinical Trials for Drugs and Biologics* (draft guidance, February 2010) and also the European Medicines Agency guidance *Reflection Paper On Methodological Issues In Confirmatory Clinical Trials Planned With An Adaptive Design* (October 2007). This study is an adaptive study, following advice depicted in these guidance documents from regulatory agencies regarding studies on drugs at the current stage of development of this compound.

1.5 Subject Population

The study population for Part 2 of the study includes adult patients between the ages of 18 and 70, inclusive, male or female with a historical diagnosis of T1DM at least 12 months prior to Screening, who were diagnosed with T1DM before the age of 40 years, Subjects must have HbA1c at Screening in the range of 7—9.5% (inclusive).

1.6 Study Treatment

Drug supplies will consist of 400 mg TTP399 and matching placebo tablets for oral administration.

TTP399 or matching placebo tablets will be packaged in 60 cc HDPE bottles with heat induction seal and child-resistant closures. Each bottle will contain 40 tablets.

Drug supplies should be stored at the study site in their original containers under locked, refrigerated [2° C to 8° C (36° F to 46° F)] conditions. Once dispensed to patients, medication can be stored at room temperature.

1.7 Randomization

Randomization by site is done in this study, so that each site is randomized separately. Investigators will assign a unique patient screening identification number sequentially to each patient who has signed the informed consent document. This identifying screening number will be retained throughout the duration of study participation.

At the time of randomization, patients are assigned a unique, randomization number based on site-based randomization scheme.

Part 2 introduces a stratification into the randomization to control balance between patients who enter the study on CGM and those who do not:

There are two strata:

- Patients currently on CGM with at least 2 months of experience with personal CGM without significant interruptions (i.e. > 2 consecutive weeks) prior to screening who agree to continue using their personal CGM throughout the study in addition to the Sponsor supplied CGM.
- OR patients currently not using a personal CGM prior to screening who agree not to use a personal CGM during the study

Patients will be randomized, in balanced allocation within each stratum, to one of the following treatment groups:

- **TTP399 800 mg QD**
- Placebo QD.

Approximately 90 patients will be randomized following once daily dosing regimens:

Table 1. Study Treatment Regimen

| Regimen (planned number of patients) | Dosing Regimen | Number of TTP399 400 mg tablets | Number of TTP399 Matching Placebo tablets |
|--|------------------|------------------------------------|---|
| A (n=45) | Placebo | 0 | 2 |
| B (n=45) | 800 mg QD TTP399 | 2 | 0 |

1.8 Study Design

Each part of the study will have a screening period, a baseline period, an open label dose escalation phase (Sentinels Phase only) and a double-blind, placebo-controlled treatment period (Part 1 and 2, randomized 1:1 to placebo or TTP399). Part 1 and Part 2 will have an insulin dose adjustment period, if needed. Sentinel and Part 1 patients will have unblinded CGM the entire study and will be contacted by the site routinely to assess

safety. In Part 2 there will be two periods of sponsor provided (blinded) CGM. In addition to site visits, patients will be contacted throughout the study to assess safety as outlined in the Schedule of Activities. Phone calls are preferred, but texts are allowed. Pharmacokinetic samples will be collected throughout the study for all patients. A planned interim analysis may occur approximately 6 weeks after approximately 30 patients have been randomized in Part 1.

Each patient enrolled in Part 2 of the study will undergo screening procedures, a 2-week single-blind run-in period, a 12-week, double-blind treatment period, and a follow-up site visit. The study includes a total of up to 9 outpatient visits to the study site. Patients will visit the clinic for screening, undergo a basal insulin adjustment period of up to 3 weeks (if needed), have a single-blind placebo-run-in period, and then return to the clinic for visits on Days 1, 14, 42, and 84 for safety and efficacy assessments, followed by a safety follow-up evaluation 7 to 10 days following the final dose of double-blind study medication.

At Screening, patients will sign the Informed Consent Form and then be assessed for study eligibility.

Patients who are deemed eligible based on procedures completed at Screening will undergo a basal insulin adjustment period (if needed), and then they will return to the site at Week -2 for a placebo run-in period of at least 13 days in duration.

Randomization will occur on Day 1. Eligibility will be confirmed, and eligible patients will be randomized.

Patients will come to the study site for all site visits following an overnight fast (except water). When fasting is required, patients who do not meet the fasting requirement will not have blood or urine samples collected for laboratory assessments, but all other procedures will be carried out; those patients will be asked to return the next morning after an overnight fast for laboratory assessments.

[figure not shown]
The first dose of study medication during each treatment period will be administered at the site immediately after enrollment (for the placebo run-in) or randomization (for the

double-blind treatment period). Patients will self-administer study medication (TTP399 or placebo) at home, with the exception of the morning doses administered on the first day of placebo run-in or the first day of double-blind medication, which will be administered by study staff. Morning dosing should occur at approximately the same, just prior to the morning meal.

Patients must return to the site approximately 7 to 10 days following the final dose of clinical trial material for a follow up visit. At this visit, final procedures will be completed, and the patient will be discharged from the study.

A depiction of the study design is given in Figure 1.

Figure 1. Study Design

The study is conducted at multiple sites in the U.S.

The overall structure of the study includes the following periods:

Screening: Screening procedures include obtaining informed consent and evaluations to determine eligibility for study participation. All screening procedures should occur within two weeks of the next visit (either basal insulin dose-adjustment or Week -2). .

Basal Insulin Dose Adjustment Period (Insulin Adjustment Visit): Once a patient has met all the entry criteria at the screening visit, the site will schedule a visit to determine if the patient's basal insulin dose needs to be optimized. If the patient is on a closed loop system for automated insulin delivery (e.g. MiniMed 670G) , then the basal adjustment period (up to three weeks) is required following the patient turning off the auto mode. If the patient is a new inpen™ (hereafter in this document called to as InPen) user, the basal adjustment period (up to three weeks) is also required.

Placebo-run-in Period (ending on Day 1 with first dose administration of double-blind treatment): During the placebo-run-in and baseline period, which begins at Week -2 prior to the administration of the first dose of double-blind trial medication, patients arrive at the site to receive single-blind placebo and to have Baseline assessments, including blood samples for clinical laboratory tests and for evaluation of concentrations (pharmacokinetics; PK).

Double-blind Treatment Period (Day 1 though Week 12): It is noted that “week 12” and “day 84” are used interchangeably in this study, defining a month as 28 days and a week as 7 days. During the double-blind treatment period, daily doses of oral, double-blind study medication are administered. Efficacy, dosing compliance, and safety assessments are taken, including vital signs, adverse events, electrocardiography, and concomitant medications. Blood draws are taken for PK evaluations and for biomarkers.

Follow-up Visit (7-10 days after last dose): Approximately 7 to 10 days following the last dose of study medication, final safety assessments are taken, including vital signs, adverse events, ECG, and concomitant medications.

1.9 Sample Size and Power Considerations

The protocol includes sample size considerations for Part 2 of the study. The Part 1 of the study is considered to be a pilot study within the adaptive study protocol to obtain initial placebo-controlled, double-blind study data to support the progression of the investigation to Part 2.

The following statements pertain to sample size determination for Part 2:

“Assuming a standard deviation (SD) of 1%, 34 patients per group will provide 80% power to detect a difference between a group treated with TTP399 and the group treated with placebo of 0.7% in HbA1c using alpha = 0.049.

“Randomization of 68 patients (34 patients randomized to each arm) will provide adequate power for this study to meet its objectives related to HbA1c changes.

“Assuming 30% or fewer placebo-treated patients show improvement in HbA1c of 0.3% or better and assuming 60% or more patients treated with TTP399 will achieve improvement in HbA1c of 0.3% or better by Week 12, 49 patients per group will provide 80% power to detect a difference between TTP399 and placebo. Randomization of N=120 patients into the study to be included in the Part 2 analyses provides adequate power to achieve study objectives related to responder analysis.

“It is noted that the randomization stratification for part 2 will be reflected in the randomization identification with a stratum digit.

“It is noted that in this adaptive study, modification is permitted. (Section 10.2 of study protocol).

Rigorous calculations for the required sample size for the non-inferiority aspect of the study relative to the required sample size to achieve a conclusion of non-inferiority were not done during the development of the protocol. Using a non-inferiority margin of 0.3% (from the FDA guidance entitled Guidance for Industry Diabetes Mellitus: Developing Drugs and Therapeutics Biologics for Treatment and Prevention (CDER; February 2008), the sample size required for non-inferiority is bracketed by the sample size required for adequate power for superiority of HbA1c.

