- Change from baseline total daily insulin dose
- Percent change from baseline in total daily insulin

3. ADAPTIVE STUDY DESIGN AND RATIONALE:

This adaptive study to evaluate TTP399 as a potential treatment for T1DM will occur in three parts (sentinels, learning phase (Part 1) and confirming phase (Part 2)) with the opportunity to modify the study. Weekly dose escalations (anticipated from 400mg to 1200 mg daily doses of TTP399) will occur in up to 6 sentinel patients on CSII and CGM (open label) to determine the dose to be compared with placebo in approximately 120 Type 1 diabetes patients using either CSII or MDI (with a goal of approximately 30 patients in Part 1 and approximately 90 patients in Part 2). Some possible adaptations envisioned include dose regimen, endpoints and number of patients randomized into Part 1 and 2. The study population will consist of patients with T1DM who have experience using either CSII or MDI. Patients will be dosed daily with TTP399 (orally) or placebo during the treatment period. Continuous Glucose Monitoring will be used to monitor safety and efficacy and mixed meal tolerance tests will be conducted in sentinel patients. Pharmacokinetic samples will also be obtained.

The three parts of this an adaptive Phase 1b/2 study are:

[figure not shown]
- Sentinel phase: an open label, dose escalation with approximately 6 adult T1DM patients (sentinels) with up to 8 visits,
- Part 1: a placebo-controlled study with approximately 30 randomized adult type 1 diabetic patients dosing for 12 weeks with up to 10 visits and
- Part 2: a placebo-controlled study with approximately 90 total randomized adult type 1 diabetic patients with up to 9 visits.

The analysis of the sentinel phase suggested positive results based on our progression rationale (Section 3.4.1), so Part 1 was initiated. Part 2 will be initiated upon completion of approximately 50% of patients in Part 1 in the absence of safety concerns resulting from ongoing safety review of accruing data. Completion of Part 1 and 2 will result in approximately 120 patients dosing for 12 weeks. Consented patients who have met screening criteria when the enrollment goals are met will be allowed to continue until up to a total number of approximately 140 patients are enrolled in the study.

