A sufficient number of study participants will be screened and admitted in order to randomize approximately 90 study participants into Part 2 from up to 20 sites. Patients who have met screening criteria when the enrollment goals are met will be enrolled until up to a total of approximately 140 patients enrolled in Part 1 and 2. The study population will consist of patients with T1DM who have experience using either CSII or MDI (Part 2). Patients enrolling in Part 2 are NOT required to have experience with CGM, however, patients enrolling in the study currently on personal CGM are required to have at least 2 months of experience with CGM without significant interruptions (i.e. > 2 weeks) prior to screening and agree to continue using their personal CGM throughout the study in addition to the sponsor provided CGM. If patients are not using personal CGM at screening, they should agree to not start any personal CGM during the study.

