10.2. Sample Size Determination

Assuming a standard deviation (SD) of 1%, 34 patients per group will provide 80% power to detect a difference between a group treated with TTP399 and the group treated with placebo of 0.7% in HbA1c using alpha = 0.049.

Randomization of 68 patients (34 patients randomized to each arm) will provide adequate power for this study to meet its objectives related to HbA1c changes.

Assuming 30% or fewer placebo-treated patients show improvement in HbA1c of 0.3% or better and assuming 60% or more patients treated with TTP399 will achieve improvement in HbA1c of 0.3% or better by Week 12, 49 patients per group will provide 80% power to

detect a difference between TTP399 and placebo. Randomization of N=120 patients into the study to be included in the Part 2 analyses provides adequate power to achieve study objectives related to responder analysis.

It is noted that the randomization stratification for part 2 will be reflected in the randomization identification with a stratum digit.

It is noted that in this adaptive study, modification is permitted.

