1.2 Meta-analysis

This statistical analysis plan (SAP) is for the Part 2 of the study. The analysis of the sentinel phase suggested positive results, resulting in Part 1 being initiated. Part 2 was initiated following positive results from an analysis of Part 1. Completion of Parts 1 and 2 is anticipated to result in approximately 110 patients dosed for 12 weeks.

The intention for this study is that Part 1 subjects (dosed for 12 weeks) and Part 2 subjects (dosed for 12 weeks) will be combined in a meta-analysis using a methodology following the analysis plan for the meta-analysis, which will be similar to the methodologies specified in the SAPs for Part 1 and for Part 2. It is noted that the intention for the integrated analysis is specified in the study protocol, Section 10.4. No alpha is allocated to the meta-analysis; however, it was the intention from the design stage of this study.

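### SAP 1.9 credits N=120 to the Part 2 responder objective, but Part 2 plans 45 per arm, below the plan's own 49, and the primary composite responder was not powered

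*SAP*

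**What the plan says.** SAP 1.9 introduces its sample-size text as applying to Part 2 and then quotes protocol 10.2. For HbA1c superiority it gives 34 per group (difference 0.7%, SD 1%, alpha 0.049, 80% power). For a responder defined as an HbA1c improvement of 0.3% or better, at 30% on placebo and 60% on TTP399, it says "49 patients per group will provide 80% power". It then concludes: "Randomization of N=120 patients into the study to be included in the Part 2 analyses provides adequate power to achieve study objectives".

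Other sections give the planned numbers:

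- SAP 1.7: "Approximately 90 patients will be randomized following once daily dosing regimens". Its Table 1 shows n=45 in each arm.
- Protocol section 3: "Completion of Part 1 and 2 will result in approximately 120 patients dosing for 12 weeks".
- SAP 1.2: "Completion of Parts 1 and 2 is anticipated to result in approximately 110 patients dosed for 12 weeks", and of pooling the two parts, "No alpha is allocated to the meta-analysis".

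On responders, SAP 6.1.2 lists the 0.3% fall as a secondary variable, and SAP 7.6.2 gives secondary categorical endpoints Fisher's exact test. SAP 6.1.1 makes a different, composite responder primary. SAP section 2 lets superiority on treatment responders, together with non-inferiority on HbA1c, satisfy the primary endpoint.

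On non-inferiority, SAP 1.9 discloses that rigorous sample-size calculations were not done. With a margin of 0.3%, it then says "the sample size required for non-inferiority is bracketed by the sample size required for adequate power for superiority of HbA1c".

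**The concern.** The number credited to the responder objective is not the number in the analysis that SAP 1.9 describes. The planned Part 2 size also falls short of the requirement stated one sentence earlier.

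The paragraph also powers a responder that is not the one in the primary analysis. No rates, size or power are given for the composite, so nothing in the plan shows what Part 2 can detect on an endpoint that can decide primary success.

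The non-inferiority sentence states no true difference, and its truth depends on one. This matters mainly when the responder test is the route to success. If HbA1c superiority is shown, non-inferiority follows automatically. If it is not, the HbA1c benefit may be small.

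**Working it through.** **Inputs.** Two-sided alpha 0.049 (SAP 7). Rates 0.30 and 0.60, SD 1% and difference 0.7% (SAP 1.9). Part 2 size 45 per arm (SAP 1.7, Table 1). Margin 0.3% with a 95% confidence interval (SAP 2). All figures assume that the stated number is evaluable.

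**1. Reproducing the plan's 49.** With mean rate 0.45, z = 1.969 for alpha 0.049 and z = 0.842 for 80% power:

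- Uncorrected: n = [1.969·√(2·0.45·0.55) + 0.842·√(0.30·0.70 + 0.60·0.40)]² / 0.30² = 42.2, so 43 per arm.
- Continuity-corrected: (42.2/4)·[1 + √(1 + 4/(42.2·0.30))]² = 48.7, so 49 per arm.

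The plan's 49 is the continuity-corrected size. It agrees with Fisher's exact test, which first reaches 80% at 48 per arm.

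**2. Where 120 comes from.** 30 (Part 1) + 90 (Part 2) = 120, or 60 per arm over both parts. Part 2 alone has 90/2 = 45 per arm, which is 49 − 45 = 4 short.

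**3. Power for the 0.3% responder.** For Fisher's test, sum the products of the two binomial probabilities over all outcome pairs whose exact p-value is at most 0.049.

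| Per arm | Fisher power | Basis |
|---|---|---|
| 40 | 72.5% | assumption: (110 − 30)/2 |
| 45 | 75.3% | SAP Table 1 |
| 49 | 81.5% | plan's requirement |
| 55 | 84.6% | assumption: (140 − 30)/2 |
| 60 | 89.4% | the N=120 claimed |

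At 45 per arm an uncorrected chi-square gives 81.8%.

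**4. HbA1c superiority.** Two-sample t-test, non-centrality 0.7/√(2/n). At 34 per arm power is 80.9%, which reproduces the plan. At 45 per arm it is 90.6%.

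**5. Non-inferiority.** The non-centrality is (0.3 + benefit)/(SD·√(2/n)), where benefit is the true HbA1c advantage of TTP399. At 45 per arm and SD 1%:

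| True benefit | Power |
|---|---|
| 0 | 29% |
| 0.1 | 47% |
| 0.2 | 65% |
| 0.3 | 80% |
| 0.7 | 99.7% |

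For 80% power the benefit must be about 0.39 at 34 per arm, or 0.30 at 45 per arm. At a benefit of 0.7 only 17 per arm are needed, so the bracketing sentence holds at the section's own effect. The SAP gives no residual SD for the covariate-adjusted model, and a smaller SD helps: at no difference, power is 42% with SD 0.8% and 80% with SD 0.5%.

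**6. The composite responder, side by side.**

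| Item | One place | Another place |
|---|---|---|
| HbA1c criterion | SAP 5.3: stable or improved | SAP 6.1.1: change below zero |
| Ketones | SAP 5.3: no treatment-emergent abnormal beta-hydroxybutyrate | SAP 6.1.1: same in substance |
| Lactate | SAP 5.3: no criterion | SAP 6.1.1: no treatment-emergent value above range |
| Hypoglycemia | SAP 5.3: no increase in episodes below 54 | SAP 6.1.1: no severe episode |
| Test | SAP 7.6: Fisher's exact test | SAP 7.6.1: logistic regression, supported by Mantel-Haenszel |

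No responder rate is given for either definition.

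**The case against.** - **The sentence may mean the pooled analysis.** It speaks of randomization into the study, and protocol 10.6.1 names an integrated analysis of both parts. It may be loosely worded protocol text carried over. That does not rescue it in SAP 1.9, which places it under Part 2. SAP 1.2 leaves pooling to a separate analysis without alpha and now expects about 110 patients, not 120.
- **A reader might infer that the SAP presents Part 2 as 60 per arm throughout.** It does not: Table 1 in SAP 1.7 prints 45 for each arm. The fault is a contradiction between two sections.
- **A reader might infer that Part 2 is underpowered for its primary purpose and needs more patients.** The documents do not support this. The shortfall is 4 per arm against an approximate target, the power depends on the test, and the 0.3% responder appears in none of Evaluations 1 to 7. HbA1c superiority exceeds its 80% target.
- **Enrolment could run higher.** Protocol 5.3 says patients "will be enrolled until up to a total of approximately 140 patients enrolled in Part 1 and 2". That is a ceiling, not a plan. The synopsis counts up to 6 sentinels within it, which leaves (140 − 36)/2 = 52 per arm, and in Part 2 enrolment precedes randomization.
- **A reader might call the bracketing sentence an arithmetic error.** It is an unstated assumption that holds at a benefit of 0.7, and it follows an open statement that rigorous calculations were not done.

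**Conclusion.** The contradiction stands. SAP 1.9 credits 120 patients to a Part 2 responder objective that has 45 per arm, below the plan's own 49. Under the Fisher test that SAP 7.6.2 assigns, power is about 75%, not the roughly 89% implied by 60 per arm. This rests on the plan's 60% and 30% rates, alpha 0.049 and no loss of evaluable patients; with an uncorrected test it is about 82%.

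The consequence for gated conclusions is small, because the endpoint concerned is secondary and outside the testing sequence. The more important gap is the composite responder. It can decide primary success, but it was not powered, and its definition and test each differ between two places in the SAP. The non-inferiority wording needs its assumed benefit stated and no more.

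**What to change.** Do not add patients.

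1. Leave the protocol quotation in SAP 1.9 as it is and add a correction after it, listed in SAP 1.11: the Part 2 responder test has about 45 per arm. Give the power of the 0.3% responder as about 75% with Fisher's test and label that endpoint secondary.
2. Before unblinding, first reconcile the responder definitions in SAP 5.3 and 6.1.1. Then choose one primary test between SAP 7.6 and 7.6.1, and state that the composite was not powered.
3. Add one sentence to the non-inferiority paragraph: with margin 0.3% and SD 1%, 80% power assumes a true HbA1c benefit of about 0.4 at 34 per arm or 0.3 at 45 per arm, and power at 45 per arm is about 29% if there is no difference.

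The cost is wording in SAP 1.9 and 1.11 (and in protocol 10.2 if it is amended), one reconciled definition and one choice of test. The stated power becomes less favourable, but the design and conduct do not change.
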